1.3.2.2 Evaluation of Tumour Response

Tumour response will be evaluated by the site investigator and by an independent central review. The central review will be the data used for all imaging efficacy endpoints. Response and progression will be evaluated using the revised RECIST guideline (v1.1) and CCI [REDACTED]. Only subjects with measurable disease at baseline, who have received at least one cycle of therapy, and have had their disease re-evaluated will be considered evaluable for response.

All measurable lesions up to a maximum of two lesions per organ and five lesions in total, representative of all involved organs, should be identified as target lesions and recorded and measured at baseline. Target lesions should be selected on the basis of their size (lesions with the longest diameter), be representative of all involved organs, and permit reproducible repeated measurements. On occasion, if the largest lesion does not permit reproducible measurement, the next largest lesion which can be measured reproducibly will be selected. A sum of the diameters (longest for non-nodal lesions, short axis for nodal lesions) for all target lesions will be calculated and reported as the baseline sum diameters. If lymph nodes are included in the sum, then only the short axis will be added into the sum. The baseline sum of diameters will be used as reference to further characterise any objective tumour regression in the measurable dimension of the disease.

All other lesions (or sites of disease) including any measurable lesions over and above the five target lesions should be identified as nontarget lesions and should also be recorded at baseline. Measurements of these lesions are not required, but the presence, absence, or unequivocal progression of each should be noted throughout follow-up.

Overall objective tumour response will be classified as CR, PR, SD or PD, and unevaluable according to RECIST v1.1 at each visit. Based on objective tumour response, BOR, ORR, DoR and DCR will be calculated for both the central and the investigator review.

Time to PFS according to RECIST v1.1 will also be summarised.

Details of the response evaluation will be given in a separate image review charter.

CCI

1.3.2.3 Quality of Life Questionnaire - QoL

A Quality of Life Questionnaire, composed of a general questionnaire for oncological subjects (QLQ C30; 28 items with a 4-point scale and two items with a scale from one to seven) and a NET-specific questionnaire (GI.NET21; 20 items with a 4-point scale) in paper-form will be completed at baseline (Visit 1, predose), during treatment at Visits 2 and 3 (predose), and at the EOCT /EOAC /EW Visit. It is important that the investigator does not influence the subject's responses to the questionnaire in any way.

1.3.3 Safety assessments

1.3.3.1 Adverse Events

Adverse events are defined as any untoward medical occurrence in a subject or clinical trial subject administered a medicinal product, which does not necessarily have a causal relationship with this treatment. An AE can therefore be any unfavourable and unintended sign (including an abnormal laboratory finding), symptom, or disease temporally associated with the use of a medicinal (investigational) product, whether or not considered related to the medicinal (investigational) product.

Adverse events will be monitored from the time that the subject gives informed consent and throughout the study, and will be elicited by direct, nonleading questioning or by spontaneous reports.

By definition, all AEs are regarded as 'treatment emergent', i.e. not seen before treatment or, if already present before treatment, worsened after start of treatment.

Natural progression or deterioration of NETs including symptoms or malignancy under study will be recorded as part of the efficacy evaluation and should not be recorded as an AE/SAE. Death due to disease progression will be recorded as part of the efficacy evaluation and will not be regarded as an SAE. Neuroendocrine tumour status will be monitored through RECIST v1.1 evaluation and completion of Quality of Life Questionnaires (QLQ C-30 and GINET.21). Signs and symptoms should not be reported as AEs/SAEs if they are clearly related to a relapse or an expected change or progression of NETs (symptoms/malignancy). These signs and symptoms should only be reported as AEs/SAEs (depending on the investigator's judgment) if they are:

- Judged by the investigator to be unusually severe or accelerated NETs or;
- If the investigator considers the deterioration of NETs signs and symptoms to be caused directly by the IRPP or OPS301 if applicable.

If there is any uncertainty about an AE being due solely to the NETs under study, it should be reported as an AE/SAE as appropriate. Preplanned or elective surgeries or therapies should be recorded in the subject's source documents but are not to be considered AEs unless there was any change to the subject's medical condition during the AE collection period.

All AEs will be assessed and documented in the eCRF by the investigator. Follow-up of the AE, after the last visit of the trial, is required if the AE or its sequelae persist. Follow-up is required until the event or its sequelae resolve or stabilise at a level acceptable to the investigator and the sponsor's clinical monitor or his/her designated representative.

Preplanned or elective surgeries or therapies should be recorded in the subject's source documents but are not to be considered AEs unless there was any change to the subject's medical condition during the AE collection period.

All AEs (including SAEs) are to be accurately recorded on the AE page of the subject's Case Report Form (CRF).

For both serious and non-serious AEs, documentation must be supported by an entry in the patient's hospital notes. The following information should be captured for all AEs: date of onset and resolution, severity of the event, assessment whether the event was serious or non-serious, Investigator's opinion of the relationship to investigational drug (OPS201 or OPS301), treatment required for the AE, action taken with IRPP or OPS301 if applicable, and information regarding resolution/outcome.

Each event will be graded for severity using the classifications of CTCAE v5.0. For events not addressed in the CTCAE v5.0 (as appropriate), classifications the following grading will apply:

- Mild (Grade 1) - Mild; asymptomatic or mild symptoms; clinical or diagnostic observations only; intervention not indicated.
- Moderate (Grade 2) - Moderate; minimal, local or noninvasive intervention indicated; limiting age-appropriate instrumental Activity of Daily Living (ADL).
- Severe (Grade 3) - Severe or medically significant but not immediately life-threatening; hospitalization or prolongation of hospitalization indicated; disabling; limiting self-care ADL.
- Life-threatening (Grade 4) - Life-threatening consequences; urgent intervention indicated.
- Death (Grade 5) related to AE.

The relationship of an AE to IRPP administration will be classified according to the following:

- ***Related:*** reports including good reasons and sufficient information (e.g. plausible time sequence, dose response relationship, pharmacology, positive dechallenge and/or rechallenge) to assume a causal relationship with IRPP administration in the sense that it is plausible, conceivable or likely.
- ***Not related:*** reports including good reasons and sufficient information (e.g. implausible time sequence and/or attributable to concurrent disease or other drugs) to rule out a causal relationship with IRPP administration.

The relationship of the study treatment to an AE will be determined by the investigator and subsequently reviewed by the sponsor.

1.3.3.2 *Serious Adverse Events*

An SAE is classified as any untoward medical occurrence that at any dose:

- Results in death, or;
- Is life threatening, that is any event that places the subject at immediate risk of death from the event as it occurred. It does not include an event that, had it occurred in a more severe form, might have caused death, or;
- Requires inpatient hospitalisation or prolongation of existing hospitalisation, excluding admission for social or administrative reasons (see further), or;
- Results in persistent or significant disability / incapacity, where disability is a substantial disruption of a person's ability to conduct normal life functions, or;
- Is a congenital anomaly / birth defect in the offspring of a subject who received the IRPP or OPS301 if applicable;
- Is an important medical event that may not result in death, be life threatening, or require hospitalisation when, based upon appropriate medical judgement, may jeopardise the subject and may require medical or surgical intervention to prevent one of the outcomes listed in this definition. Examples of such medical events include allergic bronchospasm requiring intensive treatment in an emergency room or at home, blood dyscrasias or convulsions that do not result in in-patient hospitalisation, or the development of drug dependency or drug abuse.

In addition to the above criteria, any additional AE that the sponsor or an investigator considers serious should be immediately reported to the sponsor and included in the safety database. This includes any suspected or confirmed coronavirus COVID-19 (SARS-CoV-2) infection (seriousness criteria should be “other medically significant” if no other seriousness criteria are present (e.g. hospitalisation).

Planned hospitalisations that occur exclusively for study procedures must not be documented as SAEs.

1.3.3.3 *Clinical Laboratory Tests*

The certified laboratory of the study site will perform haematology, biochemistry and urinalysis laboratory tests. Pituitary markers will be analysed at local laboratory unless this assessment cannot be performed locally, it will be analysed in a central laboratory. CCI

A copy of the laboratory certification and tabulation of the reference ranges will be provided.

1.3.3.3.1 Hematology

Haematology parameters include haemoglobin, haematocrit, mean corpuscular volume, mean corpuscular haemoglobin, white blood cell count (total and differential: leukocytes, neutrophils, eosinophils, basophils, lymphocytes, monocytes), red blood cells and platelets.

Haematology will be measured at the Screening Visit, at Visits 1 to 3 and optional Visits 4 and 5 (predosing, 24±1 hour (Day 2), 48±1 hour (Day 3), 72 to 96 hours (Day 4 to 5), 144 to 168 hours (Day 7 to 8) and Day 15±2 days), Follow-up Visits, the EOCT/EOAC/EW Visit and the visits in the 2-year long-term follow-up period.

1.3.3.3.2 Blood Biochemistry

Biochemistry parameters include sodium, potassium, chloride, calcium, glucose, creatinine, urea, albumin, total bilirubin, AST, ALT, alkaline phosphatase, GGT, C-reactive protein. Creatinine clearance will also be calculated.

The eGFR value will be calculated by the Modification of Diet in Renal Disease (MDRD) formula.

Biochemistry will be measured at the Screening Visit, at Visits 1 to 3 and optional Visits 4 and 5 (predosing, 24±1 hour (Day 2), 48±1 hour (Day 3), 72 to 96 hours (Day 4 to 5), 144 to 168 hours (Day 7 to 8) and Day 15±2 days), Follow-up Visits, the EOCT/EOAC/EW Visit and the visits in the 2-year long-term follow-up period.

1.3.3.3.3 Urinalysis

Urinalysis parameters include specific gravity, pH, protein, glucose, blood, urobilinogen, erythrocytes, leukocytes, ketones, bilirubin, nitrite, albumin.

To be measured at the Screening Visit, predose and Day 15 at Visits 1 to 3 and optional Visits 4 and 5, Day 7 to 8 at Visit 1, at Follow-up Visits 1 to 3, at the EOCT/EOAC/EW Visit, and at the visits in the 2-year long-term follow-up period.

1.3.3.3.4 Pregnancy test

Prior to each PRRT cycle (Screening Visit, Visits 1 to 3 and optional Visits 4 and 5, predosing) each female subject of childbearing potential must undergo a pregnancy test. A serum pregnancy test will be performed at the Screening Visit. A serum or urine pregnancy test will be performed predose on Day 1 of Visits 1 to 3.

In the event of pregnancy, the subject is not allowed to receive further PRRT cycles and must be withdrawn from the study. The pregnancy must be reported to the sponsor on the SAE form until the end of the trial.

1.3.3.3.5 Pituitary Marker (Marker of Pituitary Function)

Pituitary markers include free thyroxine (fT4), cortisol, insulin-like growth factor (IGF)-1 and thyroid stimulating hormone (TSH). These markers results will not be included in the summary statistics if subjects are receiving substitute or therapy concerning the respective pituitary axis (e.g. no analysis of fT4 and TSH in subjects who receive thyroxine, no analysis of cortisol in subjects who received corticosteroids).

Measured predose at Visit 1, Day 1 at 08:00 (±1 hour) and Visit 1, Day 2 – important to judge cortisol value, and at the EOCT/EOAC/EW Visit.

1.3.3.4 *Physical Examination*

A physical examination (including examination of general appearance, skin, neck (including thyroid), eyes, ears, nose, throat, heart, lungs, abdomen, lymph nodes, musculoskeletal, cardiovascular and nervous systems) will be carried out by a physician at Screening and each study visit up to, and including, the EOCT/EOAC/EW Visit and the visits in the 2-year long-term follow-up period. Any clinically significant abnormalities at Screening will be noted on the medical history pages of the eCRF. During the study, if in the opinion of the investigator there are any clinically significant changes in the physical examination findings (abnormalities), they will be recorded as AEs.

1.3.3.5 *Height and Weight*

Subject height will be measured at the Screening Visit, while weight will be assessed pre-dose at Visits 1-3 (and optional Visits 4 and 5) and at the EOCT/EOAC/EW Visit. Body surface area (BSA) will be determined with the Mosteller formula [2].

Height and weight and associated calculated parameters, will be summarised together with the vital signs.

1.3.3.6 *Vital Signs*

Body temperature and supine vital signs (blood pressure and heart rate) will be measured on the nondominant arm after 5 minutes of supine rest at the following time points: at the Screening Visit, at Visits 1 to 3 and optional Visits 4 and 5 (predose, postinfusion: at stop of infusion (0), 30±5 minutes, 60±10 minutes, 4 hours ±10 minutes, 24±1 hour (with the exception of Visit 1: 08:00/Day 2 corresponds approximately 18 to 20 hours), 48±1 hour (Day 3), 72 to 96 hours (Day 4 to 5), 144 to 168 hours (Day 7 to 8), Day 15, Follow-up Visits, the EOCT/EOAC/EW Visit and the visits in the 2-year long-term follow-up period.

1.3.3.7 *Electrocardiography*

A 12-lead ECG will be performed at the Screening Visit, predose at Visits 1 to 3 and optional Visits 4 and 5, at the Follow-up Visits, at the EOCT/EOAC/EW Visit and at the visits in the 2-year long-term follow-up period. ECGs will be recorded in triplicate and in the supine position after at least 5 minutes of rest.

During the administration of the PRRT study drug, starting with the injection of the antiemetic (i.e. 15 to 30 minutes before the start of the amino acid infusion), a 24 hour ECG (Holter) will be recorded to monitor cardiac safety during the treatment.

The site will be required to review ECGs as a safety check at each Day 1 before administration. This will be done immediately by a qualified investigator at the study site. ECG and Holter assessments will be reviewed centrally during the core trial period and local review at the site will be performed during visits in the 2-year long-term follow-up period. Results will be provided to the site and retained as source data.

1.3.3.8 *Performance Status*

The performance status of the subjects will be defined by the Karnofsky scoring and assessed at the Screening Visit, pre-dose at Visits 1-3, pre-dose at optional Visits 4-5 and at the EOCT/EOAC/EW Visit.

- 100 - Normal; no complaints; no evidence of disease,

- 90 - Able to carry on normal activity; minor signs or symptoms of disease,
- 80 - Normal activity with effort; some signs or symptoms of disease,
- 70 - Cares for self; unable to carry on normal activity or to do active work,
- 60 - Requires occasional assistance but is able to care for most of his personal needs,
- 50 - Requires considerable assistance and frequent medical care,
- 40 - Disabled; requires special care and assistance,
- 30 - Severely disabled; hospital admission is indicated although death not imminent,
- 20 - Very sick; hospital admission necessary; active supportive treatment necessary,
- 10 - Moribund; fatal processes progressing rapidly,
- 0 – Dead.

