1.7 Risk-benefit Assessment

As many radiopharmaceuticals are excreted rapidly in the urine, the absorbed dose to the wall of the urinary bladder is often large compared with the absorbed dose to other organs and tissues exposed to the same study dose [45]. In the urinary bladder wall and liver, the estimated absorbed doses (8.2 and 10.9 Gy, respectively) at the anticipated highest cumulative administered activity (3 \times 7.4=22.2 GBq) are far lower than the radiation dose limit thresholds in the published literature (35 Gy for liver and 60 Gy for urinary bladder wall) [46].

Another factor that may potentially affect the development of haematological toxicity is radiation exposure to the spleen. As the spleen is part of the immune system, it can produce

blood cells and act as a major reservoir for red, white blood cells and platelets [47, 48, 49]. It is reported to be the organ that receives the highest mean absorbed dose of all organs during PRRT [50, 51], partly because of the presence of somatostatin receptors on lymphocytes [52, 53]. A dose dependent relationship may exist between the total absorbed dose to the spleen and the blood cell count [54]. In the spleen, the estimated absorbed dose is 66.6 Gy at the anticipated highest administered activity ($3 \times 7.4 = 22.2$ GBq). However, there are no known radiation dose limits described in the literature.

Another potential risk is toxicity to other organs expressing somatostatin receptors (sstr2), such as the pituitary gland and pancreas as these organs are also potentially targeted by PRRT [55, 56, 57]. Therefore, it is not unlikely that patients treated with PRRT maybe are at risk of developing hormone disturbances or deficiencies during their follow-up period. To monitor any adverse effect on organs expressing sstr2, specific markers will be measured at each cycle during the study. For example, specific markers of the function of the hypothalamic-pituitary-adrenal axis, thyroid stimulating hormone (TSH), cortisol and IGF-1 will be measured at baseline, on Day 1 of each cycle and Day 2 of the first cycle and at the end of the core trial. Blood glucose will also be monitored.

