8.2.5 Pituitary Marker (Marker of Pituitary Function)

Pituitary markers include free thyroxine (fT4), cortisol, insulin-like growth factor (IGF)-1 and thyroid stimulating hormone (TSH). These markers will not be analysed if subjects are receiving substitute or therapy concerning the respective pituitary axis (e.g. no analysis of fT4 and TSH in subjects who receive thyroxine, no analysis of cortisol in subjects who received corticosteroids).

Measured predose at Visit 1, Day 1 at 08:00 (±1 hour) and Visit 1, Day 2 – important to judge cortisol value, and at the EOCT/EOAC/EW Visit.

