3.2.1.3 Laboratory data

A separate listing of normal ranges for SI and local laboratories units will be provided by study site laboratory, gender and age where relevant.

Laboratory data (including hematology, biochemistry, pituitary markers and urinalysis) will be listed in SI and local laboratories units and abnormal values will be flagged (High, [H], Low [L], clinically significant [C], CTCAE version 5.0 grade (G)) where applicable. Any unscheduled laboratory assessments will be flagged [U] in the listings. In addition, a listing of clinically significant abnormal values will be presented.

As multiple local laboratories are used within the study, a data normalisation method (refer to [Appendix 1: Derived Data](#), and Ref. 5, 6, 7) will be used before summarising the data. The normalized lab data values will be also included in the lab data listings together with the reference normal range limits used for the normalisation.

(a) Hematology, Biochemistry and Pituitary Markers

For hematology, biochemistry and pituitary marker parameters, the baseline will be defined as the last measurement collected prior to the first dose of study drug.

For hematology, biochemistry and pituitary marker parameters, summary statistics, by study part, cohort (part B only) and overall, will be presented at each scheduled assessment for normalised actual values and changes from baseline. For pituitary markers, all values will be displayed in a listing, however the summary tables may exclude any results if it was drawn while the subject was receiving medication that may have been deemed to impact the result.

The determination of the medications impacting the result will be based upon medical monitor review and reflected in a footnote.

Shift tables from Baseline to worst post-baseline and also, each post baseline visit. In the shift tables, the number and percentages of subjects with low, normal, or high values will be presented by study part, cohort (part B only) and overall.

For hematology and biochemistry, summary statistics by study part, cohort (part B only) and overall, will be also provided for nadir and day to nadir by cycle (time from cycle baseline to nadir during the same cycle) and on lab toxicities after start of study medication with worst CTCAE version 5.0 Grades 3 and 4 (refer to Appendix 1, Derived data).

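### The pituitary-marker exclusion does not separate therapy present at first dose from replacement started on study, so the marker summaries can lean towards no pituitary effect

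*SAP*

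**What the plan says.** Pituitary markers (fT4, cortisol, IGF-1, TSH) are part of the primary safety endpoint (protocol 3.2.1, SAP 3.1.1). Protocol 1.7 gives the reason for measuring them: treated patients may be "at risk of developing hormone disturbances or deficiencies during their follow-up period".

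Three places state what happens to results from subjects on therapy for an axis:

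- Protocol 8.2.5: "These markers will not be analysed if subjects are receiving substitute or therapy concerning the respective pituitary axis".
- SAP 1.3.3.3.5: "These markers results will not be included in the summary statistics if subjects are receiving substitute or therapy concerning the respective pituitary axis", with the examples "no analysis of fT4 and TSH in subjects who receive thyroxine, no analysis of cortisol in subjects who received corticosteroids".
- SAP 3.2.1.3: "For pituitary markers, all values will be displayed in a listing", but the summaries "may exclude any results if it was drawn while the subject was receiving medication that may have been deemed to impact the result". On which drugs count: "The determination of the medications impacting the result will be based upon medical monitor review and reflected in a footnote".

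SAP 3.2.1.3 plans summary statistics and changes from baseline at each scheduled assessment, and shift tables (low, normal, high) from baseline both to the worst post-baseline value and to each post-baseline visit. SAP 3.2.15 bases percentages on non-missing observations. SAP section 5 does not list the different wording as a change from the protocol.

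**The concern.** Leaving out fT4 and TSH measured on thyroxine, or cortisol measured on a steroid, is reasonable in itself: such values do not describe the subject's own axis. The difficulty is timing. Replacement present at first dose is a baseline characteristic. Replacement started after dosing may be a consequence of the harm the markers are there to detect. None of the three passages separates the two, so exclusion can depend on the outcome, and it removes deficient subjects rather than unaffected ones.

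At stake is whether the marker summaries for a named risk can be read at face value. Someone using them to judge pituitary safety, by cohort or overall, could see few or no shifts to abnormal and not know that the relevant late results had been set aside.

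**Working it through.** The plan gives no figure to reproduce and no incidence of deficiency. The check is a comparison of passages, followed by an illustration.

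**1. The three rules side by side**

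| Place | Force | Unit excluded | Who decides |
|---|---|---|---|
| Protocol 8.2.5 | mandatory, no analysis | subject and axis, while on therapy | not stated |
| SAP 1.3.3.3.5 | mandatory, left out of summary statistics | general rule while on therapy; examples worded by subject, no time limit | not stated |
| SAP 3.2.1.3 | optional, all values listed | single result drawn on the medication | medical monitor, with a footnote |

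None refers to whether therapy began before or after first dose.

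**2. What sampling leaves**

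Protocol 8.2.5, SAP 1.3.3.3.5 and the schedule tables put pituitary samples at Visit 1 Day 1 (predose), Visit 1 Day 2 and the EOCT/EOAC/EW visit. Protocol Table 9 also counts three samples in the core trial. Protocol 1.7 instead describes sampling on Day 1 of each cycle. Under the first schedule, one late core-trial value exists, nominally at Week 24.

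**3. Tracing a subject who becomes deficient after Visit 1 Day 2**

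- Deficiency first found in the EOCT sample and treated afterwards: under SAP 3.2.1.3 the low value predates treatment and is kept.
- Replacement started before the EOCT sample: the EOCT result may be excluded. The subject then has no late value in the change-from-baseline or by-visit shift table and, with non-missing denominators, leaves the percentage as well. In the worst-post-baseline table, result-level exclusion leaves the Day 2 value, so the subject can appear as normal.
- Same subject, EOCT result kept: it may look normal because of the replacement. Retention alone does not show the deficiency either.

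No planned pituitary table counts newly started replacement as an abnormal outcome.

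**4. Illustration of direction (all incidences assumed)**

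Let k of n subjects become deficient, and let a fraction f of those be replaced before the late sample and excluded. The apparent rate is k(1 − f)/(n − kf).

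- n = 55 (planned maximum), k = 3, f = 0: 3/55 = 5.5% (Clopper-Pearson 95% CI 1.1% to 15.1%). With f = 1: 0/52, upper limit 1 − 0.025^(1/52) = 6.8%.
- n = 55, k = 5, f = 0: 9.1% (3.0% to 20.0%). With f = 1: 0/50, upper limit 7.1%.
- One cohort of n = 10, k = 2: 20.0% at f = 0, 1/9 = 11.1% at f = 0.5, 0/8 at f = 1.

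The f = 1 rows assume that every case is replaced before the late sample and that the subject leaves the table completely. Partial exclusion shrinks the bias without reversing it.

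**5. Corticosteroids**

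Protocol 6.3.3 includes dexamethasone in the antiemetic scheme before the amino acid infusion, unless contraindicated, with site regimens and short-term steroids allowed from version 6.0. Taken literally, the cortisol example in SAP 1.3.3.3.5 could remove cortisol for many subjects, who have no replaced axis at all.

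**The case against.** The strongest reply is that SAP 3.2.1.3 is the operative section, while 1.3.3.3.5 sits in the chapter that restates the protocol. Under 3.2.1.3 exclusion is optional, applies to single results, is footnoted, and leaves every value in a listing. Replacement normally follows an abnormal sample, so much of the evidence would predate treatment and be kept. A laboratory abnormality requiring intervention is reportable as an adverse event (protocol 8.1.2.4), TEAEs are tabulated by preferred term and worst grade (SAP 3.2.1.2), and the replacement drug enters the concomitant-medication frequency table (SAP 3.2.12.1). The study is descriptive, with no formal testing. Moreover, 3.2.1.3 mentions summary tables generally; that the shift tables are included is an inference.

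Most of this stands, and it limits the point. A reader might infer that a subject with an induced deficiency disappears from the safety reporting, or that every treated case is lost. The documents do not support that. Complete removal follows only from the by-subject wording of the 1.3.3.3.5 examples, and the other reporting routes remain open. Loss under 3.2.1.3 needs replacement to start between Day 2 and the late sample with no earlier abnormal value entering the tables; the SAP does not say whether unscheduled values enter the shift tables.

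The reply does not repair the marker summaries. The other routes depend on investigator reporting and coding, the list of interfering drugs is not prespecified, and no marker table records the new replacement.

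**Conclusion.** The point holds for the pituitary marker summaries only. As written, the exclusion can depend on a post-dose event that treatment may cause. With a single late core-trial sample under protocol 8.2.5 and SAP 1.3.3.3.5, it can take a deficient subject's late result out of the change-from-baseline and by-visit shift tables. The direction is towards no pituitary effect. The size cannot be stated, because the documents give neither the incidence nor how often replacement would precede the late sample; 3/55 reading as 0/52 is the assumed extreme, not an estimate.

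The three passages also differ in force and unit. The two sampling schedules (protocol 1.7 against protocol 8.2.5 and SAP 1.3.3.3.5) contradict each other and must be reconciled; which one applies determines how many late values there are to lose.

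**What to change.** Put one rule in SAP 1.3.3.3.5 and 3.2.1.3, consistent with protocol 8.2.5:

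1. Exclude an axis entirely only for subjects on therapy for it at first dose.
2. For replacement started after first dose, keep all values drawn before it, leave values drawn on it out of the means, and keep the subject in the shift-table denominator under a separate worsened category, new replacement started. Identify these subjects from the recorded indication, not drug class alone.
3. Do not count short-course antiemetic steroids as replacement. For these, exclude only cortisol samples drawn while the steroid could affect the result.
4. Report the number excluded per marker and visit, with the reason.
5. Reconcile the sampling schedules in protocol 1.7 and 8.2.5, and in SAP 1.3.3.3.5.

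The analysis changes cost SAP wording and a derived flag. Concomitant medication and its indication are already recorded (protocol 6.3.6). The added work is a short medical review of the indication for each flagged subject, since thyroxine or a steroid may have been given for other reasons.
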